3. STUDY DESIGN

3.1 DESCRIPTION OF THE STUDY

Study YO39309 is a multicenter, open-label, Phase III clinical study with randomized and non-randomized arms designed to investigate the efficacy, safety, and pharmacokinetics of emicizumab in patients with hemophilia A regardless of FVIII inhibitor status.

Seventy patients aged ≥ 12 years who received episodic therapy with FVIII or bypassing agents prior to study entry and experienced at least 5 bleeds over the prior 24 weeks will be randomized in a 2:2:1 ratio (see [Figure 1](#)) to the following regimens:

- Arm A: Emicizumab prophylaxis at 3 mg/kg QW subcutaneously for 4 weeks, followed by 1.5 mg/kg QW subcutaneously
- Arm B: Emicizumab prophylaxis at 3 mg/kg QW subcutaneously for 4 weeks, followed by 6 mg/kg Q4W subcutaneously

- Arm C: No prophylaxis (control arm)

In addition, 15 pediatric patients with hemophilia A and inhibitors who received episodic therapy with bypassing agents prior to study entry will be enrolled to Arm D:

- Arm D: Emicizumab prophylaxis at 3 mg/kg QW subcutaneously for 4 weeks, followed by 1.5 mg/kg QW subcutaneously

The endpoints will be analyzed separately for the two randomized emicizumab arms (Arms A and B): 1.5 mg/kg QW and 6 mg/kg Q4W, as well as for the additional arm in pediatric patients (Arm D): 1.5 mg/kg QW.

Randomized patients will be stratified according to the number of bleeds the patient experienced over the 24 weeks prior to study entry—less than versus greater than or equal to 9—to ensure a balance of patients with lower versus higher number of bleeds in all arms.

To ensure a representative variety of patients with hemophilia A enrolled in this study to investigate the efficacy and safety profile of emicizumab in both inhibitor and non-inhibitor adolescent and adult populations, enrollment of up to 55 non-inhibitor patients will be permitted.

Emicizumab is intended for prophylactic use only (i.e., not to treat bleeds that have already occurred). The primary efficacy analysis, defined as comparing the number of bleeds over time for patients randomized to receive prophylactic emicizumab versus no prophylaxis will be conducted at the earliest timepoint when all randomized patients (Arms A, B, and C) have either completed 24 weeks in the study or discontinued from treatment. For Arm D, the primary efficacy analysis will be conducted after the last enrolled patient has completed 24 weeks in the study or discontinued from treatment. Therefore, there will be a range of observation periods from 6 to approximately 12 months, or longer. Randomized patients will be enrolled globally from China and other countries. At least 60 patients will be enrolled from China.

[figure not shown]
Arm D will only enroll patients from mainland China.

To obtain additional safety and efficacy data on emicizumab, patients who are randomized to Arm C (control arm with no prophylaxis) will have the opportunity after 24 weeks to switch to receive emicizumab prophylaxis at the 6 mg/kg Q4W dosing regimen (emicizumab prophylaxis at 3 mg/kg QW subcutaneously for 4 weeks, followed by 6 mg/kg Q4W). This regimen was chosen to enhance the safety and efficacy data obtained on this dosing regimen because there will be less data available on this regimen from the global studies than from the 1.5 mg/kg QW regimen.

After completing at least 24 weeks of treatment with prophylactic emicizumab, patients who receive emicizumab prophylaxis (Arms A, B, or C after treatment switch and Arm D)

and derive clinical benefit will be allowed to continue emicizumab as part of this study as long as they continue to derive clinical benefit and emicizumab is still in clinical development (see Section 4.3.4). There will be an extension phase in this study for all patients who complete at least 52 weeks of treatment with prophylactic emicizumab and still deriving clinical benefit. The study will be extending for 3 years after the last Arm D patient completes 1 year of treatment *and patients still having clinical benefit are transferred to a post-trial continued access solution per Roche Global Policy on Continued Access to Investigational Medicinal Products (see Section 4.3.4). The study will end earlier, before 3 years after the last Arm D patient completes 1 year treatment, should the post-trial continued access solution be available earlier.* Those who are well controlled after 24 weeks on emicizumab (<2 spontaneous and clinically significant bleeds) will continue treatment on their assigned emicizumab regimen; whereas, those who experience suboptimal control (≥ 2 spontaneous and clinically significant bleeds) will have the option to escalate to 3 mg/kg QW per investigator's judgement after consulting with the Medical Monitor.

Figure 1 Study Schema

BR=bleed rate; mo=month.

During the study, individual bleeds will be captured as they occur, while HRQoL, health status, patient safety, and days of school or work missed will be assessed as outlined in the schedule of assessments (Appendix 1-A and Appendix 1-B). Patients (or their caregiver) will be asked via an electronic, handheld device to report their bleeds (i.e., start date and time, reason, type, location, and associated symptoms for joint and muscle bleeds) and hemophilia-related medication use (i.e., start date and time, reason, type and dose of injection). The bleed/medication questionnaire should be completed whenever a bleed or medication use occurs. In the event of no bleed or medication use, the patient should complete the questionnaire at least once a week to serve as

confirmation that no bleed or medication use occurred. In addition, health status information will be collected whenever a bleed is reported.

Throughout the study, biomarkers related to thromboembolism (e.g., D-dimer, prothrombin 1 + 2 fragment) and emicizumab trough concentrations will be collected as per the schedule of assessments. Immunologic biomarkers (i.e., anti-emicizumab antibodies and anti-FVIII antibodies) will also be measured (see [Appendix 2](#)).

Exploratory PD biomarkers (e.g., aPTT, FVIII activity, thrombin generation assay) will be collected as per the schedule of assessments. As values for some of these tests are normalized by low plasma concentrations of emicizumab, a variety of assay formats (one stage, chromogenic) and modifications (pre-dilution of patient plasma) will be investigated for assessment of PD response at higher emicizumab plasma concentrations. However, it is not expected that these biomarkers will be used to guide dosing or the selection of patients to be treated with emicizumab. Rather, these biomarkers may be used to identify a future assay for the monitoring of emicizumab activity. In addition, factor IX (FIX) and FX antigen levels will be measured.

Physical examinations, vital signs assessments, ECGs, and laboratory assessments will be collected as per the schedule of assessments and will be the same for all patients, with the exception that emicizumab PK and ADAs will not be measured in patients in Arm C prior to switch to emicizumab treatment. Adverse events will be captured as they occur for the duration of the study.

All patients who receive emicizumab in the study will undergo PK assessments. Based on clinical experience in the ongoing Phase I/II clinical studies with the treatment of over 80 breakthrough bleeds in patients receiving emicizumab with either FVIII or bypassing agents, FVIII, aPCC, or rFVIIa do not interfere with emicizumab PK assessments and no safety signals have been observed when breakthrough bleeds were treated with standard-of-care regimens during Phase I and Phase I/II studies. Therefore, no washout period is required prior to first emicizumab dose in this study, with the exception of patients who were previously receiving ITI in whom a 72-hour washout period is required prior to the first emicizumab administration.

However, in the ongoing Phase III Study BH29884 (adolescent and adult patients with hemophilia A with FVIII inhibitors), three thrombotic microangiopathy and three thromboembolic events were observed in 5 patients on emicizumab who concomitantly used on average, cumulative doses of >100 units/kg/24 hr for 24 hours of aPCC for the treatment of breakthrough bleeds. There was an additional thromboembolic event, which was a device occlusion without concomitant aPCC and assessed by the investigator as being unrelated to emicizumab (see [Section 1.2](#), [Section 1.3](#), [Section 5.1.2.1](#), and [Section 5.1.3](#)). Although FVIII and aPCC are fundamentally different in their potential interaction with emicizumab, investigators should keep in mind

that circulating emicizumab increases patients' coagulation potential. Therefore, it is recommended that:

- Breakthrough bleeds should be treated with the lowest FVIII or rFVIIa dose expected to achieve hemostasis, which may be lower than the patients' prior dose. Investigators should review with patients the dose to be used to treat breakthrough bleeds.
- The use of aPCC/PCC or other bypassing agents should be avoided or limited (see Section 4.4.1).
- Investigators and patients should consider objective verification of bleeds.

Also, local laboratory assessments are required to monitor the risk for thromboembolic events or thrombotic microangiopathy as per the schedule of assessments (see Section 4.5.5 and [Appendix 1-A](#)).

Patients might require dosing with FVIII or bypassing agents for the treatment of potential breakthrough bleeds, especially for the time period until steady-state concentrations of emicizum

ab have been reached. The reason for the use of coagulation products will be documented (e.g., bleeding, prophylaxis). The number of infusions needed to treat the bleed will be derived from the medication log.

Of note, a non-interventional study (Study BH29768) has been initiated to document the number and types of bleeds and current treatment with episodic or prophylactic bypassing agents, as well as collect information on HRQoL, health status, and safety in patients with hemophilia A (including children < 12 years of age). The assessments in the non-interventional study will mitigate the risk of inaccurate reporting of bleeds that may occur with historical data collection and may provide data collected prospectively for over 24 weeks. Patients who are enrolled in the non-interventional Study BH29768 are eligible to enroll in this study, provided they meet the eligibility criteria and are able to enroll at a participating site while the study is open for enrollment.

Investigators will contact the Medical Monitor in the event of suspected lack or loss of efficacy of emicizumab in order to discuss potential laboratory evaluations (e.g., anti-emicizumab antibodies, coagulation tests) to be performed as well as to re-evaluate their patient's benefit-risk of continued treatment.

Collection of PK/ADA/Biomarker samples from Arm D patients will stop when the patient completes the study or after Week 49, whichever occurs first.

A schedule of assessments is provided in [Appendix 1 A](#), [Appendix 1 B](#), [Appendix 2 A](#), [Appendix 2 B](#), [Appendix 2 C](#), and [Appendix 2 D](#).

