4.4.1 Permitted Therapy

Concomitant use of the following drugs and therapies will be permitted:

- Drugs intended to control bleeds, including FVIII products or bypassing agents as standard-of-care episodic treatment. Exact dosages will not be specified in the study; however, investigators should consider that circulating emicizumab may increase patients' coagulation potential. Investigators should review with patients the dose to be used to treat breakthrough bleeds. Breakthrough bleeds should be treated with the lowest FVIII or rFVIIa dose expected to achieve hemostasis, which may be lower than the patients' prior FVIII or rFVIIa dose.

Caution should be taken for patients who are using rFVIIa (e.g., consideration of using no more than 90 µg/kg of rFVIIa as an initial dose).

Use of aPCC/PCC in combination with emicizumab should be avoided completely in patients who have the option of using other bypassing agents to treat bleeds. In the event that aPCC/PCC is the only available bypassing agent, the lowest dose expected to achieve hemostasis should be prescribed, with no more than 50 units/kg of aPCC/PCC to be administered as an initial dose.

Other bypassing agents (e.g., Byclot[®]) should be avoided. In cases where such agents are the only available bypassing agent, the lowest dose expected to achieve hemostasis should be prescribed, with no more than the lowest dose described in the prescribing information to be administered as an initial dose (e.g., no more than 60 µg/kg of Byclot[®]).

Exact dose and schedule of bypassing agents should be discussed with patients at the beginning and throughout the study. Repeated dosing of rFVIIa, aPCC/PCC, or other bypassing agents should be performed only under medical supervision, which includes laboratory monitoring by additional local laboratory assessments (see [Appendix 1-A](#)), and consideration should be given to verifying bleeds prior to repeated dosing.

Caution should be taken if anti-fibrinolitics are used in conjunction with rFVIIa in patients receiving emicizumab.

- Drugs and therapies to treat adverse events and use of topical antiseptics, anesthetics, eye drops, etc., that are not considered to result in systemic exposure
- Drugs to treat an existing medical condition ongoing at study entry that do not violate the eligibility criteria (e.g., anti-retroviral therapy for HIV infections)
- Local anesthetic cream for emicizumab SC administration

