4.5.5 Laboratory, Biomarker, and Other Biological Samples

Local laboratory assessments will be performed as indicated on the schedule of assessments. When study drug administration is scheduled on days of clinic visit, laboratory samples should be drawn before the administration of study drug. Laboratory assessments will include the following:

- Hematology (hemoglobin, hematocrit, platelet count, RBC count, WBC count, absolute differential count [neutrophils, eosinophils, lymphocytes, monocytes, and basophils], mean corpuscular volume, mean corpuscular hemoglobin, mean corpuscular hemoglobin concentration, and RBC distribution width)
- Serum chemistries (sodium, potassium, glucose, blood urea nitrogen, creatinine, calcium, phosphorus, magnesium, total and direct bilirubin, albumin, alanine aminotransferase, aspartate aminotransferase, and alkaline phosphatase)

- In patients who receive bypassing agents, the following local laboratory tests will be performed within 24–48 hours of initial bypassing agent use so the investigator may monitor for potential thromboembolic events and thrombotic microangiopathy:

- Platelet count
- Serum creatinine
- Lactate dehydrogenase (LDH)
- Peripheral blood smear analysis to evaluate for schistocytes

A plasma sample should also be provided for laboratory monitoring of:

- Fibrinogen
- D-dimer

For patients who require multiple doses of bypassing agents, local laboratory monitoring should be performed every 24–48 hours thereafter until 24–48 hours following the last dose of bypassing agents administered to treat a given bleed. If applicable, laboratory results should be recorded on the Unscheduled Visit eCRFs.

- Pregnancy test: All women of childbearing potential (including those who have had a tubal ligation) will have a serum pregnancy test at screening and within 7 days prior to initiation of study medication, if applicable.

Urine pregnancy tests will be performed at specified subsequent visits. If a urine pregnancy test result is positive, it must be confirmed by a serum pregnancy test.

The following samples will be sent to the Sponsor or a designee for centralized analysis:

- Plasma samples for PK analysis
- Plasma samples for immunogenicity assessment (ADA)
- Serum and plasma for PD and exploratory PD biomarker assessments (aPTT, PT, FVIII activity, and others as listed in [Appendix 2](#))

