5.1.2 Risks Associated with Emicizumab

5.1.2.1 Identified Risks

Thrombotic Microangiopathy (Associated with Emicizumab and aPCC)

Thrombotic microangiopathy is a very rare, but serious condition whereby microvascular thrombosis leads to organ damage.

As of October 2018, among 417 patients in five studies (ACE002JP, BH29884, BH29992, BH30071, and BO39182), there were 3 patients (1.0%), all in Study BH29884, who experienced thrombotic microangiopathy while receiving emicizumab prophylaxis. These events are believed to be caused by an interaction between emicizumab and aPCC, as all 3 patients received cumulative doses of >100 U/kg/day on average of aPCC for ≥24 hours for the treatment of breakthrough bleeds just prior to developing symptoms. These events were reported as serious adverse events (two Grade 4 events and one Grade 3 event). One patient died due to a serious adverse event of Grade 4 rectal haemorrhage (assessed as unrelated to emicizumab). From additional analyses, including data on the thrombotic microangiopathy and thromboembolic events,

there is evidence to support a drug-drug interaction between aPCC and emicizumab. Please see the Emicizumab Investigator's Brochure for a complete summary of safety information.

Specific guidance regarding the use of bypassing agents in combination with emicizumab is detailed in Section 4.4.1.

Any thrombotic microangiopathy event should be reported as an adverse event of special interest and also as a serious adverse event, if it meets criteria for such (see Section 5.2.2 and Section 5.2.3).

Guidelines for management of patients who develop thrombotic microangiopathy are provided in Section 5.1.3.

Hypercoagulation and Risk of Thrombosis

As of October 2018, four thromboembolic events have been reported in 3 patients with hemophilia A with inhibitors while receiving emicizumab in Study BH29884.

Two patients who administered cumulative doses of > 100 U/kg/day on average of aPCC for ≥24 hours while receiving emicizumab developed thromboembolic events. The thromboembolic events were reported as serious adverse events (Grade 3 cavernous sinus thrombosis, Grade 3 skin necrosis, and Grade 2 thrombophlebitis superficial); however, none were life-threatening or fatal. No anticoagulation was started and symptoms in both patients improved with supportive care. These adverse events are believed to be caused by a drug-drug interaction between emicizumab and aPCC.

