Appendix 1-A (cont.) Schedule of Assessments

Schedule of Assessments—Arm C (Screening to Switch to Emicizumab)								
	Screening ^a	Wk 1	Wk 5	Wk 9	Wk 13	Wk 17	Wk 21	Daily/weekly ^b
Informed consent ^e	x							
Inclusion/exclusion criteria	x							
Medical history and demographics ^f	x							
Physical examination (including weight) ^g	x	x						
Vital signs ^h	x	x ^h	x	x	x	x	x	
Height	x							
Serum pregnancy test ⁱ	x	x						
Urine pregnancy test ⁱ		x						
Concomitant medications ^j	x	x	x	x	x	x	x	
ECG ^k	x	x ^k						
Safety laboratory assessments ⁱ	x ⁱ	x						
Anti-FVIII antibodies	x							
Bleed medication questionnaire ^l								x
Bleed/injection data review ^s		x	x	x	x	x	x	
Adverse events ^m		x	x	x	x	x	x	
HRQoL and health status ^o		x			x			
PD biomarkers assessment ^q		x						

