Appendix 1-A (cont.) Schedule of Assessments

Schedule of Assessments—Arm C (Continued, at Time of Switch to Emicizumab)																		
	Wk 25	Wk 26	Wk 27	Wk 28	Wk 29	Wk 31	Wk 33	Wk 37	Wk 41	Wk 45	Wk 49	Q12W from Wk 61	Wk 73	Wk 85	Daily/weekly ^b	Study Comp/ET ^c	Early Disc. Safety F/U Visit before Study Comp ^d	
Physical examination (including weight) ^g	x				x						x			x			x	x
Vital signs ^h	x ^h	x	x	x	x		x	x	x	x	x ^h	x	x ^h	x		x ^h	x	
Height	x										x		x					
Serum pregnancy test ⁱ	x																	
Urine pregnancy test ⁱ	x				x		x	x	x	x	x	x	x	x		x	x	
Concomitant medications ^j	x				x		x	x	x	x	x	x	x	x		x	x	
ECG ^k	x				x ^k						x						x	
Safety laboratory assessments ⁱ	x	x	x	x	x	x	x	x	x	x	x	x	x	x		x	x	
Bleed/medication questionnaire ^l															x			
Bleed/medication data review ^s	x				x		x	x	x	x	x	x	x	x		x	x	
Adverse events ^m	x	x	x	x	x	x	x	x	x	x	x	x	x	x		x	x	
IMP management ⁿ	x	x	x	x	x	x	x	x	x	x	x	x	x	x		x		
HRQoL and health status ^o	x						x				x		x	x		x		
Emicizumab administration ^p	x	x	x	x	x		x	x	x	x	x	x	x	x				
PK/PD/ADA assessment ^q	See Appendix 2-A for details																	
Following treatment with bypassing agents ^r	Monitoring for thromboembolic events and thrombotic microangiopathy ^r																	

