Appendix 8 (cont.): WHO Toxicity Grading Scale for Determining the Severity of Adverse Events

OTHER PARAMETERS (continued)				
Local Reaction	tenderness or erythema	induration < 10 cm or phlebitis or inflammation	induration > 10 cm or ulceration	necrosis
Mucocutaneous	erythema; pruritus	diffuse, maculo-papular rash, dry desquamation	vesiculation, moist desquamation, or ulceration	exfoliative dermatitis, mucous membrane involvement or erythema, multiforme or suspected Stevens- Johnson or necrosis requiring surgery

Appendix 9

Guidelines for Dosing and Monitoring Bypassing Agents for Patients on Emicizumab

The use of bypassing agents is not expected in hemophilia A patients without inhibitors. For completeness, this appendix includes guidelines provided for treatment of breakthrough bleeds in patients with inhibitors. Careful consideration of the risks and potential benefits is advised when combining emicizumab, factor VIII (FVIII), and bypassing agent.

Drugs intended to control bleeds, including bypassing agents, should be used at the lowest dose expected to achieve hemostasis. Given that circulating emicizumab may increase patients' coagulation potential, the doses required to achieve hemostasis may be lower than the FVIII or bypassing agent doses used prior to starting the study.

Caution should be taken for patients who are using recombinant activated factor VII (rFVIIa [e.g., consideration of using no more than 90 µg/kg of rFVIIa as an initial dose]).

Use of activated prothrombin complex concentrate (aPCC) or PCC in combination with emicizumab should be avoided completely in patients who have the option of using other bypassing agents to treat bleeds. In the event that aPCC/PCC is the only available bypassing agent, the lowest dose expected to achieve hemostasis should be prescribed, with no more than 50 units/kg of aPCC/PCC to be administered as an initial dose.

Other bypassing agents (e.g., Byclot®) should be avoided. In cases where such agents are the only available bypassing agent, the lowest dose expected to achieve hemostasis should be prescribed, with no more than the lowest dose described in the prescribing information to be administered as an initial dose (e.g., no more than 60 µg/kg of Byclot®).

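### For Arm C patients who switch at Week 25, the control period has no scheduled post-baseline safety laboratory value, because their pre-dose Week 25 sample is kept out of the control summaries

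*Protocol*

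**What the plan says.** Protocol Section 3.1 states that physical examinations, vital signs, ECGs and "laboratory assessments will be collected as per the schedule of assessments and will be the same for all patients". The one exception it gives is that PK and anti-drug antibodies are not measured in Arm C before the switch.

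Appendix 1-A shows something different. In the grid whose title begins "Schedule of Assessments—Arm C (Screening to Switch to Emicizumab", the safety-laboratory row is marked at screening and Week 1 and is blank at Weeks 5, 9, 13, 17 and 21. The next Arm C draw is at Week 25, in the grid that starts at the switch. Protocol Section 4.5.5 and the notes to Appendix 1-A both place blood draws before dosing on a dosing day, so that sample is taken before the first emicizumab dose.

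Protocol Section 6.5 puts Arm C safety data into the control summaries up to the day before the switch, and reports data from the switch date onward separately. Section 6.5 and SAP Section 4.7.3 plan laboratory summaries by arm and shift tables from baseline by WHO grade. Neither mentions that the draw schedules differ. Table 2 of the protocol lists the incidence of laboratory abnormalities as a safety endpoint for Arms A, B, C and D, under an objective that compares emicizumab with no prophylaxis. SAP Section 4.1 says the randomized comparisons will have a matching safety analysis.

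**The concern.** A shift table needs a baseline and at least one later value. For a control who switches at Week 25, the schedule gives a baseline and then nothing until the switch day, and the reporting rule removes the switch-day value from the control column. Only unscheduled draws are left. The laboratory part of the randomized safety comparison would then set regular draws in Arms A and B against almost no control data, although a sample that reflects 24 weeks without prophylaxis has been taken.

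The stake is the reading of one descriptive safety endpoint. Section 3.1 adds to the problem, because a reader who relies on it would believe that the arms were tested alike.

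**Working it through.** The plan gives no figure to reproduce here. The check compares the schedule with the reporting rule and then illustrates the size.

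**Draw counts** (Protocol Appendix 1-A)

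| Window | Arms A and B | Arm C control period |
|---|---|---|
| After Week 1, before Week 25 | 8 or 9 (Weeks 2, 3, 4, 5, 9, 13, 17 and 21, plus Week 7 if marked) | 0 |
| Same window plus Week 25 | 9 or 10 | 0 under Section 6.5 for a patient switching that day; 1 if the pre-dose sample counts as control |

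The Arms A and B row, in the text available, appears to be one mark short. The count is therefore given as 8 or 9, and Week 25 is taken as marked. The blanks in the Arm C row are unlikely to be lost text, because vital signs, concomitant medications and adverse events in the same grid are filled through Week 21.

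**Reporting rule applied to the Week 25 sample**

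1. The sample is drawn before the dose, so it reflects no prophylaxis.
2. The switch date is the date of that dose.
3. Section 6.5 assigns data by date, so the sample falls outside the control summaries.
4. Scheduled post-baseline control values for that patient: 0.

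**Illustration of unequal testing.** Let p be the chance that one draw shows a new graded abnormality, with draws independent. The documents give no value for p; 2% to 5% is assumed. The chance of at least one abnormality in k draws is 1 − (1 − p)^k.

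- k = 8: 1 − 0.98^8 = 14.9%; 1 − 0.95^8 = 33.7%
- k = 9: 1 − 0.98^9 = 16.6%; 1 − 0.95^9 = 37.0%
- k = 10: 1 − 0.98^10 = 18.3%; 1 − 0.95^10 = 40.1%
- k = 1: 2%; 5%
- k = 0: nothing can be seen from scheduled draws

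At p = 1% the figures for k = 8 and k = 9 are 7.7% and 8.6%. With the same underlying risk in every arm, the any-time proportions would thus differ through testing frequency alone. In a Week 1 to Week 25 shift, k = 1 in every arm and this difference disappears.

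**The case against.** **The schedule governs.** Section 3.1 itself defers to the schedule, and Appendix 1-A openly sets different schedules by arm: Arm D differs from Arms A and B, and a footnote gives Arm C its own pregnancy-test timing. No site would draw blood on the wrong day. This stands, so the Section 3.1 fault is one of wording.

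**The gap would be visible.** A reader might infer that untested controls will be tabulated as normal and the difference taken for a drug effect. The documents do not support that. The opening of Protocol Section 6 bases percentages on non-missing values and requires tables to show the population size with missing observations. SAP Section 4.3 also reports adherence to scheduled assessments. This stands too: the k = 0 line above means no data, not a reported rate of 0%. But showing the gap does not fill it, and the value that would fill it already exists.

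**Adverse event tables are barely touched.** Under Protocol Section 5.3.5.5 a laboratory result becomes an adverse event only if it has symptoms, leads to action or is judged clinically significant. Adverse events are reviewed in Arm C at Weeks 1, 5, 9, 13, 17 and 21, and unscheduled tests are allowed. This stands.

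**Bypassing agents.** The control grid also lacks the row for "Monitoring for thromboembolic events and thrombotic microangiopathy" after bypassing-agent use. A reader might infer that controls are left unmonitored against a known risk. The documents do not support that either. Section 4.5.5 begins "In patients who receive bypassing agents, the following local laboratory tests will be performed within 24–48 hours of initial bypassing agent use" and has no arm limit. The risk itself is tied to the study drug: Section 5.1.2.1 says "These events are believed to be caused by an interaction between emicizumab and aPCC", and Appendix 9 is titled "Guidelines for Dosing and Monitoring Bypassing Agents for Patients on Emicizumab". The missing row is probably deliberate, and no harm from it is shown.

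**Conclusion.** The point holds and is minor. For controls who switch at Week 25, the reporting rule as written leaves the laboratory shift comparison with no scheduled post-baseline control value, against 8 or 9 earlier draws in Arms A and B. Section 3.1 misdescribes this.

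The effect is confined to descriptive safety summaries. A reader should not infer any effect on the bleed-rate analyses, alpha or power, none of which uses these laboratory data. If someone did read untested controls as normal, the error would work against emicizumab.

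The conclusion rests on three assumptions: the Arm C grid is read correctly, controls switch at the Week 25 visit, and the pre-dose rule is followed. The percentages also rest on the assumed p and on independent draws. One limit remains: the SAP refers to the schedule in protocol version 3, which is not among the documents, so the counts come from the current protocol.

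**What to change.** 1. In Protocol Section 6.5 and SAP Section 4.7.3, assign the pre-dose laboratory sample taken on the switch day (Week 25) to the Arm C control period. It may also serve as baseline for the emicizumab period; the tables should say that it is used twice.
2. Present the between-arm laboratory shift as Week 1 to Week 25 in Arms A, B and C. Where Appendix 1-A lets a screening result from 5 days or less earlier stand in for Week 1, use that result.
3. Footnote tables of abnormalities at any time with the draw schedule of each arm.
4. Correct the exception in Section 3.1 to match the Arm C grid. ECGs and physical examinations belong in it as well, since the grid marks them only at screening and Week 1 before the switch.

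Leave the bypassing-agent text in Section 4.5.5 unchanged. Limiting it to patients on emicizumab would remove monitoring that its wording now gives controls, and so widen the difference between arms. Arm C should also stay in the laboratory comparison, because Table 2 names it for this endpoint.

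The cost is one sentence in each of the two analysis sections, a table footnote and a wording correction, with no new draws. A single Week 25 value cannot show abnormalities that came and went during the control period; that limit stays. Appendix 2-C says PK, biomarker and antibody sampling stopped in March 2021, so the control period is probably over. The Section 3.1 change would then only correct the record, while items 1 to 3 still affect any laboratory table yet to be produced.
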